3.6.6. Expected Adverse Events

Any observed response in the patch test area that can be denoted using the irritation criteria summarized in [Table 3](#) and [Table 4](#) will not be considered an AE.

Tape related reactions will only be recorded as AEs when the subject is discontinued due to tape reaction around all sites. When 1 or 2 sites are experiencing severe tape related reactions, the application site will be stopped and the subject will continue on the study. This will be noted in the database as "T" as indicated in [Table 5](#) and will be considered an expected AE. When all application sites are experiencing tape reaction, the subject is discontinued and therefore be recorded as an AE. The subject will be followed up through resolution.

3.7. Instructions for Rapid Notification of Serious Adverse Events

3.7.1. Contact person and number

Serious adverse events must be reported immediately (i.e., not later than 24 hours after first knowledge) by e-mail with the scanned TKL SAE report form to:

3.7.2. Reporting Responsibility

Any death, SAE, pregnancy, (see [Section 3.6](#)), or unusual frequency of AEs, must be reported immediately (i.e., not later than 24 hours after first learning of its occurrence) to the Sponsor's study manager by the Investigator, even if the event(s) appear to be unrelated to study treatment. Follow-up information about a previously reported SAE or pregnancy must also be reported to the Sponsor within 24 hours of receiving it. If the SAE or pregnancy has not been previously documented (i.e., is a new occurrence) and it is thought to be related to the investigational product (or therapy), the Sponsor may contact the Investigator to obtain further information. If warranted, an investigator alert may be issued, to inform all Investigators involved in any study with the same product (or therapy) that this SAE or pregnancy has been reported.

The IRB should also be notified of SAEs or pregnancies and of any follow-up information in writing, as is practical, and depending on local regulations.

3.7.3. Reporting procedures

For each SAE, the Investigator will complete a SAE Report Form in English and assess the relationship of each SAE to study treatment. The completed form(s) should be sent by e-mail to the Sponsor within 24 hours of first knowledge of the SAE (as outlined in [Section 3.7.1](#) and [Section 3.7.2](#)). The initial SAE should be reported immediately, even if only preliminary information is available. Follow-up information should be sent by the same Investigator, restating the date of the original report. Either a new SAE form is sent (stating that it is a follow-up), or the original one is resent (with the new information highlighted and a new date provided). The follow-up should describe whether the event has resolved or continues, if and how it was treated, whether the blind was broken or not, and whether the patient continued or discontinued study participation. The form confirmation will be retained.

Pregnancy follow-up (as outlined in [Section 3.6.5](#)) should be reported to the IRB within 24 hours of first knowledge on a Pregnancy Report Form. Follow up will describe the outcome of the pregnancy, including any voluntary or spontaneous termination, details of the birth, and the presence or absence of any congenital abnormalities or birth defects.

3.8. Appropriateness of Safety Measurements

The safety assessments in the study are standard safety measures in clinical trials.

4. STATISTICAL METHODS

4.1. General Considerations for Data Analysis

The focus of the statistical analysis will be the comparison of the cumulative irritation response to the investigational product with the cumulative irritation response of the controls. The primary parameter for cumulative irritancy will be the mean cumulative irritation score.

The statistical analyses described below will be supplemented by a comprehensive Statistical Analysis Plan (SAP) which will be finalized before the database is locked. Any changes to the statistical plans will be described and justified in the final report.

All statistical processing will be performed using the SAS® system (version 9.2 or higher). No interim or subgroup analyses are planned.

4.2. Sample Size and Power Considerations

The sample size of 30 evaluable subjects conforms to industry and regulatory standards for determination of dermal cumulative irritation potential.

4.3. Subject Populations for Analysis

All subjects who receive treatment will be evaluable for safety (cumulative irritancy and AEs).

4.3.1. Background and Demographic Characteristics

Descriptive statistics will be used to summarize demographic characteristics (age, gender, Fitzpatrick skin type, and race) and background characteristics for the randomized subject population. Past/coexistent medical history information for all randomized subjects will be presented in a by-subject listing.

4.3.2. Study Product/Visit Compliance

Descriptive statistics will be used to summarize study product compliance for the randomized subject population.

4.4. Prior and Concomitant Medications

Prior and concomitant medication information for all randomized subjects will be presented in a by-subject listing.

4.5. Efficacy Evaluation

This section is not applicable to this study.

4.6. Safety Evaluation

4.6.1. Cumulative Irritancy

Individual irritancy scores will be displayed in a data listing for all subjects, products, and readings, along with the mean and total of the scores.

Frequency counts of each assigned score at each reading for each product will also be presented. No data imputations are to be made for discontinued subjects or missed evaluations. However, when a patch has been discontinued due to limiting irritation, the last observed score (3) will be carried forward through all subsequent readings ([Table 3](#) and [Table 4](#)).

The primary variable of interest is the mean cumulative irritation score. The total cumulative irritation score for each subject and product will also be calculated as the sum of irritation scores. These parameters will be tested pairwise for product differences using Fisher's protected least significant differences in the context of the 2-way analysis of variance (ANOVA), including main effects of subject and product, without interaction. Pairwise differences will be tested only if the null hypothesis of a common mean score for all products is rejected at the 5% level.

Once the maximum score (combined score of a Response Symbols and Numerical equivalents and an effect on super facial layers of the skin) of a 3 or greater is achieved, the cumulative irritancy score will be calculated as the maximum score of 3 for that individual site for the remainder of the study.

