Safety Evaluation Criteria:	All local and systemic adverse events (AEs) observed by or reported to the Investigator throughout the study will be evaluated. The intensity, duration, and causal relationship to the investigational patch are to be rated for all AEs.
Statistical Methods:	Cumulative irritancy will be quantified for each subject/product by the mean and total cumulative irritancy score. This parameter will be tested pair wise for product differences using analysis of variance (subject, product).
Number of Study Centers:	Single center

Signature page

Product names: **CCP-020 (Diacerein 1%) Topical Ointment**
Vehicle

[figure not shown]
TKL Study number: **DS310717**

Sponsor protocol number: **CCP-020-102**

The signatures of the representatives on the following page constitute their approval of this protocol and provide the necessary assurances that this study will be conducted according to all stipulations stated in the protocol, including all statements as to confidentiality. It is also agreed that the study will not be initiated without the approval of an appropriate Institutional Review Board.

Approved by the following:

Sponsor

Signature page for the Principal Investigator

[figure not shown]
Product names: CCP-020 (Diacerein 1%) Topical Ointment

Vehicle

TKL Study number: DS310717

Sponsor protocol number: CCP-020-102

I have read this protocol and agree to conduct this study in accordance with all stipulations of the protocol and in accordance with the Declaration of Helsinki.

Investigators and study administrative structure

This figure consists of a 10x3 grid of horizontal bar charts. Each cell in the grid contains a black bar. The length of the bars varies, indicating data values. The bars are positioned at different heights within each cell, suggesting multiple data series or conditions per cell. The grid is defined by vertical and horizontal lines, creating a structure of 10 rows and 3 columns.

TABLE OF CONTENTS

Signature page.....	3
Signature page for the Principal Investigator.....	4
Investigators and study administrative structure.....	5
List of Abbreviations	9
1. INTRODUCTION	10
1.1. Background Information.....	10
1.2. Rationale for the Study	10
2. STUDY OBJECTIVES	12
3. INVESTIGATIONAL PLAN.....	13
3.1. Study Design.....	13
3.2. Discussion of Design	13
3.3. Study Population.....	13
3.3.1. Subject Population	13
3.3.2. Inclusion and Exclusion Criteria	13
3.3.3. Interruption or Discontinuation of Treatment.....	15

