3.4.7. Treatment Compliance

All patches will be applied and removed by investigative personnel. Whereas bathing will be allowed (low tub bath/frontal showers), the patched areas are not to be soaked and are to be kept as dry as possible, per the instructions to be given to each subject. Subjects will be instructed to contact the Investigator before starting any medication, including OTC remedies. In the case of an emergency treatment, the Investigator must be informed as soon as possible. A trained, experienced evaluator will assess study compliance.

Records of patch applications and visit schedule compliance will be recorded on the subjects' CRFs.

If individual patches become dislodged or are misplaced, such that continuous contact with the skin has been interrupted, then patching at that site must be discontinued for the remainder of the study and that patch site will be considered not complete. If all patches become dislodged, the subject will be discontinued from further participation in the study.

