3.5.5. Safety Assessments

3.5.5.1. Local Tolerability Assessments

Assessment of the patch sites will be conducted by a trained evaluator once at Baseline (Day 1) and then 21 times post baseline during the study ([Table 3](#)). There will be a main evaluator for the study; a backup evaluator will also be assigned in the event that an emergency occurs and the main evaluator is unable to attend the study visit. The following symbols and their respective numerical equivalent Grades will be used to express the response observed at the time of examination ([Table 4](#)).

Table 3: Response Symbols and Numerical Equivalents

Grade	Score*	Definition
0	0	No evidence of irritation
1	1	Minimal erythema; barely perceptible
2	2	Definite erythema, readily visible; or minimal edema; or minimal papular response
3	3	Erythema and papules
4	3	Definite edema
5	3	Erythema, edema, and papules
6	3	Vesicular eruption
7	3	Strong reaction spreading beyond test site

*Scores are utilized only during the statistical analysis process of the study. Grades will be conducted throughout the study by the trained evaluator.

Table 4: Effects on Superficial Layers of Skin

Grade	Score*	Response
A	0	Slight glazed appearance
C	1	Marked glazing
E	2	Glazing with peeling and cracking
F	3	Glazing with fissures
G	3	Film of dried serous exudate covering all or portion of the patch site
H	3	Small petechial erosions and/or scabs

*Scores are utilized only during the statistical analysis process of the study. Grades will be conducted throughout the study by the trained evaluator.

Other notations (see [Table 5](#)) may be made in place of a score to designate particular circumstances preventing the assignment of a score or in addition to a score to identify damage to the epidermis and/or spreading of a reaction beyond the patch site.

The actual patch test grades are a combination of a numerical ([Table 3](#)) and letter ([Table 4](#)) grades consistent with the definitions given in the grading scales. However, in order to determine discontinuation of a patch site (grade > 3) and to perform statistical analyses, grades containing letter grades have to be converted to numerical equivalents. These are converted as follows: A=0, C=1, E=2 and F, G, and H=3. These equivalents are considered additive to any numerical score (e.g., 2C=2+1=3), in this case the patch site would be discontinued.

Table 5: Other Notations

Notation	Definition
X	Subject absent
B	Burning or stinging sensation
PD	Patch dislodged

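### Section 4.6.1 tests a total that is a raw sum, so a dislodged or tape-stopped site with unscored readings, if kept in the analysis, has too low a total unless every missing reading would be 0

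*Combined protocol and SAP*

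**What the plan says.** Section 4.6.1 makes the mean cumulative irritation score the primary variable and adds a second parameter: "The total cumulative irritation score for each subject and product will also be calculated as the sum of irritation scores". Both are analysed: "These parameters will be tested pairwise for product differences", using Fisher's protected LSD in a subject-plus-product ANOVA. The Synopsis also pairs them: "Cumulative irritancy will be quantified for each subject/product by the mean and total cumulative irritancy score".

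On missing readings, 4.6.1 says: "No data imputations are to be made for discontinued subjects or missed evaluations". The one exception is a patch stopped for limiting irritation, where the score of 3 runs through all later readings.

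Two other routes end patching at a single site while the subject stays in the study:
- Dislodgement (3.4.7): "patching at that site must be discontinued for the remainder of the study and that patch site will be considered not complete".
- Tape reaction at one or two sites (3.6.6): "the application site will be stopped and the subject will continue on the study".

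Under 3.5.5.1 a Table 5 notation may be made "in place of a score to designate particular circumstances preventing the assignment of a score or in addition to a score". Section 4.3 makes every treated subject evaluable for cumulative irritancy. Section 3.5.1 plans 21 post-baseline scores per site. Nothing in the text prorates the total, sets a minimum number of readings, or removes an incomplete site from the test.

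**The concern.** Leaving readings out of a sum gives the same total as scoring them 0. The plan guards against this when a site stops for irritation, but not when it stops for dislodgement or tape. A stopped site with unscored readings would look less irritated than it was, simply because it was read less often.

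The total is one of two formally tested parameters. Loss concentrated on one product could create a difference in totals between like products. Loss spread over all products adds noise and could hide a real difference. The mean and the total could also disagree only because sites have different numbers of readings.

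**Working it through.** **Readings per site.** Days 2 to 21 give 20 and Day 22 gives 1, so 20 + 1 = 21, matching 3.5.1. Scores run from 0 to 3 (Tables 3 and 4; cap in 4.6.1), so a full total lies between 0 and 21 × 3 = 63.

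**One site.** After k scored readings the raw total is the sum of the first k scores. The shortfall is the sum of the 21 − k missing scores. It cannot be negative and is 0 only if all of them would be 0. For an assumed constant score s, the raw total is s × k against a full s × 21:
- s = 1, k = 7: 7 against 21.
- s = 1, k = 14: 14 against 21.
- s = 0: 0 against 0.

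The mean of scored readings is s × k / k = s in every case.

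**One product, 30 subjects, s = 1, three sites stopped.**
- At reading 7: (27 × 21 + 3 × 7) / 30 = 588 / 30 = 19.6, which is 6.7% below 21.
- At reading 14: (27 × 21 + 3 × 14) / 30 = 609 / 30 = 20.3, which is 3.3% below.

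**Effect on the test (simulation, 20,000 runs, all inputs assumed).** There are 30 subjects and four products. Site mean = product level + subject effect (SD 0.2) + residual (SD 0.3). Levels are CCP-020 1.25, vehicle 1.0, saline 0.4, SLS 2.2, flat over time and not rounded. The raw total is 21 × site mean, multiplied by k/21 at stopped sites. The test is the two-way ANOVA with protected LSD at 5%, residual df (30 − 1) × 3 = 87.

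Power, CCP-020 against vehicle:

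| Sites lost | Raw total, stop at 7 | Raw total, stop at 14 | Scored-reading mean |
|---|---|---|---|
| None | 89% | 89% | 89% |
| 3 on each of the four products | 64% | 84% | 89% |
| 3 on each product except SLS | 79% | 87% | 89% |

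With loss on all four products and a residual SD of 0.2, power goes from 99.8% to 88% (stop at 7) or 99% (stop at 14). With an SD of 0.5 it goes from 48% to 34% or 45%.

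SLS matters because, for a given stop, the extra variance is proportional to the squared level: 1.25² + 1.0² + 0.4² + 2.2² = 1.5625 + 1 + 0.16 + 4.84 = 7.5625. The SLS share is 4.84 / 7.5625 = 64%.

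False rejection, CCP-020 and vehicle identical:

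| Loss | Raw total |
|---|---|
| None | 5% |
| 3 sites of one product, level 1, stop at 7 | about 12% (SD 0.2: 18%; SD 0.5: 7%) |
| Same, stop at 14 | about 6.6% |
| 1 site of one product, level 1, stop at 7 | 5 to 6% |
| 3 sites of one product, levels 0.1 to 0.3, stop at 7 | about 5% |
| Exactly 3 on each of the four products, stop at 7 | about 1% |

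The scored-reading mean stays at about 5% in these flat-path cases.

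**Where the mean is not safe.** Take an assumed path of seven 0s, seven 1s and seven 2s, stopped after reading 10. The sum is 3 and the scored mean 0.3, against a full total of 21 and mean of 1.0. Proration gives 21 × 0.3 = 6.3. Proration therefore corrects the count of readings, not a trend over time.

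**The case against.** The strongest reply is that the chain is conditional. Section 3.5.1 has all test sites assessed, and a notation may accompany a score, so a stopped site may still yield 21 numbers, though the later ones would come from unpatched skin. The label that 3.4.7 gives a dislodged site could be meant as exclusion from the analysis, and 3.3.1 aims for 30 completed subjects. Section 4.3 points the other way, but it speaks of subjects and sets no rule for sites. Section 4.1 also promises a comprehensive SAP before database lock, which is not in the supplied text and may settle this. All of that stands. It limits the point to sites that are unscored and retained.

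A reader might infer three stronger things that the documents do not support.
- *That the primary analysis is biased by the raw sum.* The mean's denominator is not written out. But 4.6.1 lists scores "along with the mean and total of the scores" and bars imputation, which most naturally means the mean of scored readings; dividing by 21 would amount to imputing 0. On that reading the mean does not shrink with fewer readings. Its behaviour on rising or falling paths is a separate issue.
- *That about a quarter of the power is lost.* That figure needs SLS sites to be lost too, at an assumed level of 2.2. SLS sites that have already reached 3 are filled with 3 and so protected.
- *That false positives more than double.* That needs loss on only one of two like products at a level near 1. CCP-020 and vehicle share volume, pad and occlusive patch conditions (3.4.3, 3.5.1), and sites are randomized by Latin squares (3.4.5.1), so nothing suggests one-sided loss.

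What remains is that the rule as written has no answer for a stopped, unscored site that is kept, and that the resulting total is formally tested.

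**Conclusion.** The concern holds in a limited form and is minor. Where a stopped site has unscored readings and stays in the analysis, its tested total is too low unless every missing reading would be 0. That direction follows from the scale alone.

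The size does not follow from the documents, which give no rate of stopped sites, score level or SD. On the assumed inputs the effect ranges from negligible (few or late stops, or low scores) to a clear loss of power when several sites stop early, mostly through the positive control. No decision rule in the protocol rests on the total.

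**What to change.** In 4.6.1:
1. Define the mean as the sum of scored readings (observed, or 3 assigned for limiting irritation) divided by the number of scored readings.
2. Either set the tested total to 21 times this mean, or list the raw total without testing it.
3. State whether a reading taken after a dislodgement or tape stop counts as scored.
4. State whether a site labelled incomplete under 3.4.7 stays in the analysis.

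If the SAP already holds these rules, a reference to it in 4.6.1 is enough.

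The cost is a few sentences before database lock. The downside is that 21 times the mean gives the same p-value as the mean, so the total then adds no separate evidence. A repeated-measures analysis that compares products over the same readings would address trends over time; it is optional and not part of this fix.

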1.2. Rationale for the Study

This is a clinical study in-humans treated with CCP-020 (Diacerein 1%) topical ointment intended to determine the cumulative irritation potential of CCP-020 (Diacerein 1%) topical

ointment treatment on normal human skin in healthy volunteers using a cumulative irritancy patch test (CIPT) design.

Substances that come into contact with human skin need to be evaluated for their propensity to irritate with a reproducible, standardized, quantitative patch evaluation procedure that demonstrates the study material can be applied safely to human skin without significant risk of adverse reactions.²

Cumulative irritancy patch evaluation is a modified primary irritancy test, which can detect irritants that require multiple applications to cause a skin reaction. These reactions are due to direct damage to the epidermal cells and no immunologic (allergic) mechanism is involved. This procedure may detect so-called “fatiguing substances,” which are mild irritants that cause more strongly positive reactions with successive multiple skin exposure.

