CCP-020 (Diacerein 1%) topical ointment and vehicle will be applied in the amount of 0.2 mL to a 2 cm x 2 cm Webril® patch pad via Eppendorf® Combitips and then applied to the subject's skin surface as soon as possible following product application. The sterile 0.9% saline (negative control) and 0.2% SLS (positive control) will be applied to a 2 cm x 2 cm Webril® patch pad via pipette and then applied to the subject's skin surface. All 4 products will be evaluated under occlusive patch conditions by means of application to a 2 cm x 2 cm Webril® pad. The patches will be secured with hypoallergenic tape as needed.

Days 2-21

The patches will be removed 24 ± 4 hours after application. Excess study material will be removed with a tissue to avoid the transference of materials between sites by investigative personnel. Investigative personnel responsible for patch application/removal will wipe each site with distilled water. A trained and blinded evaluator will perform an assessment of all test sites for irritation symptoms immediately (within 30 minutes) following patch removal using the scoring system detailed in [Section 3.5.5](#). Scores will be entered into the data sheets by the evaluator. If the skin is not disrupted (skin irritation score ≤ 2), identical treatments and patches will be re-applied to the same test sites with investigational products and control solutions using the procedures above. Separate individuals will be responsible for evaluation of the test sites (blinded) and patch application/removal (unblinded). Individual patches may be discontinued if a reaction of a grade of 3 or greater (see [Section 3.5.5](#)) occurs at any point during the study. Further patch applications of that product on that individual subject will be terminated. A NP symbol and a score of 3 will be assigned for all subsequent days.

The procedure for removal of study materials, evaluation of test sites, and application of fresh study materials will be repeated for 20 consecutive days, for a total of 21 applications per product per subject. A total of 21 post-baseline evaluation scores will be assigned to assess cumulative irritancy.

A new tube of CCP-020 [Diacerein 1%] topical ointment and vehicle will be opened every 14 days due to qualified suitability (see [Section 3.4.2](#)).

In addition, at each of the study visits, concomitant medications and AEs will be reviewed and recorded.

Day 22 (End of Study)

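### Section 4.6.1 plans only tests of difference, so a non-significant CCP-020 versus saline or vehicle result would leave the excess irritation unbounded

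*Combined protocol and SAP*

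**What the plan says.** Section 4.6.1 sets the outcome: "The primary variable of interest is the mean cumulative irritation score". A total score per subject and product is also calculated. For both it says: "These parameters will be tested pairwise for product differences using Fisher's protected least significant differences in the context of the 2-way analysis of variance". The model has subject and product main effects without interaction. An overall test comes first: "Pairwise differences will be tested only if the null hypothesis of a common mean score for all products is rejected at the 5% level". The rest of the irritancy output is descriptive: listings of individual scores with their mean and total, and counts of each score at each reading for each product.

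Section 4.1 describes the focus as comparing the investigational product with the controls and defers further detail to a SAP to be finalised before database lock. No separate SAP text is among the documents. Section 4.2 is a single sentence: "The sample size of 30 evaluable subjects conforms to industry and regulatory standards for determination of dermal cumulative irritation potential". It gives no SD, effect size, power or precision.

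Section 2 makes determining irritation potential the primary objective. Section 1.2, writing of patch evaluation in general, describes a procedure that "demonstrates the study material can be applied safely to human skin without significant risk of adverse reactions".

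**The concern.** Against saline and vehicle, the result that favours CCP-020 is a failure to reject equality. Such a failure says that the data did not separate the two sites; it does not say how far apart they could be. Without an interval or a stated power, a reader cannot tell a precise null result from an uninformative one. For any real excess, greater residual variability raises the chance of that favourable outcome, so these two tests do not control the error that matters most for a tolerability statement, namely overlooking a real excess.

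The plan also does not say which of the six product pairs answers the objective. At stake is what the trial can conclude. The data would be sound, but the planned inference would not support a statement of low irritation.

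**Working it through.** **The plan's own figure.** The 30 subjects in Section 4.2 cannot be reproduced, because no SD, effect size, power or margin is given.

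**Inputs from the documents**
- 30 evaluable subjects (Section 4.2), each receiving all four products (Section 3.4.5.1).
- 21 post-baseline readings per site (Section 3.5.1), each scored 0 to 3 in the analysis. The mean therefore runs from 0 to 3 and the total from 0 to 21 x 3 = 63.
- Two-way ANOVA with subject and product, and a 5% overall test (Section 4.6.1).

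**Assumptions**
- Pairwise tests are two-sided at 5%, the usual form of the method; the plan does not state the pairwise level.
- Residual SD s of the per-site mean is 0.3, 0.5 or 0.8 points, equal across products, with roughly normal errors and complete readings.
- The true CCP-020 minus saline difference d is 0.3 points, equal to 0.3 x 21 = 6.3 of 63 on the total. No passage says that 0.3 is an important difference.

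**Formulas**
- Residual df = (30 - 1) x (4 - 1) = 87, so t(0.975, 87) = 1.988.
- SE of a pairwise difference = s x sqrt(2/30) = 0.2582 s.
- Least significant difference = half-width of the 95% confidence interval = 1.988 x SE.
- Chance of non-significance: noncentral t with 87 df and noncentrality d/SE.

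**Results for d = 0.3**

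| s | SE | Half-width, mean score | Half-width, total | d/SE | Non-significant |
|---|---|---|---|---|---|
| 0.3 | 0.077 | 0.15 | 3.2 | 3.87 | 3% |
| 0.5 | 0.129 | 0.26 | 5.4 | 2.32 | 37% |
| 0.8 | 0.207 | 0.41 | 8.6 | 1.45 | 70% |

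For a smaller true excess of 0.2, the last column becomes 28%, 67% and 84%. The difference detectable with 80% power is 0.22, 0.37 and 0.59 points.

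**Effect of the overall test.** A simulation of 40,000 trials per setting applied the F-test first. With SLS at least 1 point above saline and d = 0.3, the overall test rejected in 97-100% of trials and the miss rates were essentially unchanged (37% at SD 0.5, 79% at SD 1.0). With a weak SLS response of 0.3 points, they rose to 42% and 87%.

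**What the SLS comparison adds.** With CCP-020 0.3 and SLS 1.0 above saline, the same simulation found CCP-020 significantly below SLS in 100% of trials at SD 0.5 and 76% at SD 1.0. Here noise works against the product. The ceiling is loose, however. If SLS is 1.5 above saline, a product 0.9 above saline (0.9/1.5 = 60% of the way to SLS) would still be significantly below SLS in 82-100% of trials over SD 0.3 to 0.8.

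**The case against.** **The protocol never equates non-significance with no irritation.** This stands. A reader might infer that a null result is the trial's success criterion, citing the words of Section 1.2 on safe application. That sentence concerns patch procedures for substances in general, and Section 2 asks only that irritation potential be determined. The documents contain no decision rule in either direction. What can be said is that the plan leaves the inference open.

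**The SLS comparison bounds irritation, and noise does not help the product there.** This also stands. A reader might infer that nothing in the plan limits irritation and that imprecision always favours CCP-020. Both statements hold only for the saline and vehicle contrasts. The SLS test can show less irritation than a known irritant, which falls well short of showing irritation close to saline.

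**The primary outcome is designated.** It is the mean score. With complete readings the total is 21 times the mean, so its tests repeat the same ones. A reader counting six pairs on two parameters as 12 competing results would overstate the problem. It is the contrast of interest that is missing.

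**Scores are reported whatever the p-values.** Listings and frequency counts will show the level of irritation, and a site that reaches the limit is kept at the worst value: "the cumulative irritancy score will be calculated as the maximum score of 3 for that individual site for the remainder of the study". This helps a reader judge size, but gives no precision for a difference between products.

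**The SAP may add intervals.** It may, but no such text is in the documents. The promise of a SAP before lock makes the change easy to place.

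**The design and sample size are conventional.** Section 4.2 rests on this. Convention can support the number of subjects; it does not turn a null test into evidence of low irritation.

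**Conclusion.** The point holds in a limited form. The plan has only tests of difference, with no interval, margin or power, so non-significance against saline or vehicle would not bound the excess irritation. For those two contrasts, more noise makes non-significance more likely; that direction needs no assumed value.

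The size does depend on assumptions. The 3% to 70% range for a 0.3-point excess spans a negligible problem to a serious one, and the documents offer no SD with which to narrow it. Scores bounded at 0 and 3 may also depart from the normal, equal-variance model used here. The effect of missing readings was not calculated.

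The documents do not support the claim that the sponsor will report a null result as absence of irritation, only that the plan contains no safeguard against it. This should be corrected. The data would remain usable as they are.

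**What to change.** In Section 4.6.1, or in the SAP before database lock and unblinding:

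1. Name CCP-020 minus saline, minus vehicle and minus SLS on the mean score as the contrasts of interest.
2. Report each with its estimate and two-sided 95% confidence interval from the same two-way ANOVA, whatever the overall F-test shows.
3. Base the statement on irritation potential on those limits. Expect half-widths of about 0.15, 0.26 and 0.41 points at residual SD 0.3, 0.5 and 0.8.
4. State that non-significance alone will not be reported as absence of irritation.

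If the sponsor wants a formal claim of low irritation, it should justify a margin and fix it before unblinding. The choice of margin is the sponsor's and is not part of this point. Two figures may help in planning:
- For illustration, with a margin of 0.3, a true difference of 0 and a one-sided level of 2.5%, 30 subjects give 97% power at SD 0.3 and 63% at SD 0.5; 80% power at SD 0.5 would need 44.
- A rule such as requiring CCP-020 to lie closer to saline than to SLS would be permissive. If SLS is 1.5 above saline, a true 0.3 excess passes it 100%, 98% and 70% of the time at SD 0.3, 0.5 and 0.8.

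The core change costs one SAP paragraph and needs no new data. The sponsor can then no longer rest a low-irritation claim on a null test. A tight formal margin could require more subjects.
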